4.1 Intervention groups

Patients eligible for participating in the study will be evaluated 24 h after surgery for the presence of moderate to severe pain. Patients with pain (VAS 0-100 mm) ≥ 45 during a 5 m walk test are included.

The study will include the following intervention groups:

Sham cryo (sham-group): Postoperative sham cryoneurolysis of the lower extremity.

Cryoneurolysis (cryo-group): Postoperative cryoneurolysis of the superficial genicular nerves, i.e., the infrapatellar branches of the saphenous nerve (ISN) and the anterior femoral cutaneous nerve (AFCN).

Both cryoneurolysis and the sham block will be performed using ultrasound and a nerve stimulator (*see 8.2 Intervention page 11*). An injection of ropivacaine around the nerves will be administered in both groups preceding the intervention. The patient will be blinded but the anesthetist performing the intervention will be unblinded.

4.2 Number of patients

44 patients, 22 in each group (sham-group vs. cryo-group).

4.3 Number of visits to the hospital

The patients will follow the standard fast-track protocol in our specialized arthroplasty unit. There will be no additional visits at the study site.

5. Selection criteria

5.1 Inclusion criteria

- Age ≥ 18
- Primary unilateral TKA
- Ability to participate in the study (understand written and spoken Danish language, self-reported pain and satisfaction)
- Signed written informed consent form
- Pain (VAS 0-100 mm) ≥ 45 during a 5-meter walk test at 24 h (20-28h) postoperatively

5.2 Exclusion criteria

- Ongoing treatment of systemic glucocorticoids or other immunosuppressant treatment apart from inhaled steroids
- Insulin-dependent diabetes
- Pregnancy or breastfeeding*
- Mental disability that could impair a patient's decision-making capability of giving informed consent and not enabling valid data collection.
- Patients with known diagnoses of schizophrenia, ongoing psychosis, bipolar disease and/or a history of ongoing anti-psychotic treatment.
- Patients with modulated pain-reception (experience) based on other diseases or injuries, e.g. spinal cord or brain injury, severe polyneuropathies or neurologic disorders.
- Posttraumatic osteoarthritis as reason for TKA
- Bleeding disorder
- Localized infection in the treatment area

- Cryoglobulinemia, cold urticaria, paroxysmal cold haemoglobinuria, or Raynaud's syndrome
- Perioperative peripheral nerve block

*Pregnancy: No women with suspected or proven pregnancy are eligible for inclusion. The following will be considered as safe contraception: intrauterine device or hormonal contraception. For women aged between 18-50 years, a urine HCG test for pregnancy will be performed.

6. Randomization and blinding

6.1 Randomization

Using <https://www.sealedenvelope.com/>, a randomization will be carried out using 2:2 block-randomization, half of which will be allocated to the sham-group and the other half to the cryo-group.

It is not possible to perform the cryoneurolysis while being blinded. Thus, the anesthetist performing the intervention will be unblinded. However, the patient and all personnel involved in study-specific assessments will be blinded to the allocation.

Group 1: sham-group	Postoperative ultrasound guided nerve block with LA followed by sham cryoneurolysis of the superficial genicular nerves.
Group 2: cryo-group	Postoperative ultrasound and guided nerve block followed by cryoneurolysis of the superficial genicular nerves.

<https://www.sealedenvelope.com/> will generate unique randomization codes to be imported to REDCap. Two lists containing the unique randomization codes will be made and stored at the Dept. of Anesthesiology, Hvidovre Hospital.

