The effect of cryoneurolysis on knee pain has been documented in a few studies. A randomized, double-blind, sham-controlled trial found that cryoneurolysis reduced symptoms of knee osteoarthritis for up to 150 days [18]. A retrospective chart-review of 100 patients undergoing TKA found that cryoneurolysis significantly lowered LOS, reduced opioid consumption until 12 weeks after surgery, and reduced pain at the 2- and 6-weeks follow-up [19]. Another retrospective analysis in 267 patients undergoing TKA found a comparable reduction in opioid requirements, pain, and LOS in patients treated with cryoneurolysis compared with historic controls [20]. A recent RCT comparing cryoneurolysis to standard of care in 124 patients undergoing TKA found that cryoneurolysis reduced opioid consumption at 72 h, 6 weeks and 12-week follow-ups [21].

Although these findings are promising, cryoneurolysis is expensive and comprehensive, and might not be relevant in all patients receiving multimodal analgesia with COX-2 inhibitors, paracetamol, local infiltration analgesia, and high-dose steroid in a fully implemented enhanced recovery program [22, 23]. Several risk factors have been associated with a high pain response including age, gender, preoperative pain, psychological profile, and quantitative sensory testing (QST) [24-26]. However, when including postoperative pain in

the prediction of acute pain, movement-evoked pain 24 h postoperatively is the best predictor for pain the week following surgery [[name] et al. – IN PREPARATION].

Using postoperative pain 24 h after surgery as a predictor of a sustained high pain response, we hypothesized that postoperative cryoanalgesia compared to a local anesthesia (LA) block with sham cryo treatment would reduce pain in patients with moderate to severe pain following TKA 2-7 days after surgery.

2. Aim

To compare the effect of postoperative cryoanalgesia with a sham treatment consisting of LA block only on postoperative pain in the first week after surgery in TKA patients with moderate to severe pain on the first postoperative day.

3. Outcomes

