8.1.2 Anesthesia

All included patients will receive general anesthesia or a neuraxial blockade in the form of a spinal anesthesia administered at level L2-L4, by injecting 2-3 ml of hyperbaric bupivacaine 0.5%. If spinal anesthesia is performed, perioperative sedation with propofol or other sedatives is optional and done in agreement with the patient. According to local guidelines, dexamethasone 0.3 mg/kg or 1 mg/kg IV rounded up to nearest 10 mg will be administered prior to surgery to patients with a pain catastrophizing scale score ≤ 20 or > 20 , respectively [27]. A supplement of local infiltration analgesia is administered directly into the surrounding tissue of the knee at the end of surgery, according to local operating procedure.

Tranexamic acid is administered as 1 g preoperatively, 1 g 3 h postoperatively, and 1 g in the surgical ward according to local operating procedure to prevent bleeding.

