8.4.1 Pain Catastrophizing Scale

The PCS consists of 13 questions divided into three sections: rumination, exaggeration, and helplessness [27, 29, 30]. The questions are answered in accordance with a scale of 0 to 4. At Hvidovre Hospital all patients undergoing major lower limb arthroplasty fill out this form prior to surgery.

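### PCS (≤20 vs >20) sets background dexamethasone and reflects a named pain risk factor, yet it is neither a stratification factor nor a covariate in the primary analysis: precision and interpretability suffer, validity does not

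*Combined protocol and SAP*

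**What the plan says.** - **Allocation.** Section 6.1 says that "a randomization will be carried out using 2:2 block-randomization", in equal proportions, and names no stratification factor. It adds: "Two lists containing the unique randomization codes will be made and stored at the Dept. of Anesthesiology, Hvidovre Hospital". It does not say what distinguishes the two lists and does not call them strata. Section 4.2 gives 44 patients, 22 per arm.
- **Background steroid.** Section 8.1.2 says that "dexamethasone 0.3 mg/kg or 1 mg/kg IV rounded up to nearest 10 mg will be administered prior to surgery", the choice depending on a "pain catastrophizing scale score ≤ 20 or > 20". The higher mg/kg figure goes with the higher score.
- **Eligibility.** Sections 5.1 and 5.2 set no PCS limit, so both groups enrol. Entry requires VAS of at least 45 on walking at about 24 h, that is, after the dexamethasone.
- **Availability of PCS.** "At Hvidovre Hospital all patients undergoing major lower limb arthroplasty fill out this form prior to surgery" (Section 8.4.1, Pain Catastrophizing Scale). Section 8.4 lists PCS among the trial data, and Section 14 lists it among the items taken from the patient record after consent.
- **Relevance to pain.** "Several risk factors have been associated with a high pain response including age, gender, preoperative pain, psychological profile" (Section 1.1). The same section counts high-dose steroid as part of multimodal analgesia.
- **Analysis.** Section 7.2 tests the primary endpoint with an unadjusted t-test or Mann-Whitney test. It allows univariate or multivariate analyses where appropriate, but names no covariate and does not tie them to the primary endpoint.

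**The concern.** One pre-randomisation variable marks two things that plausibly affect the primary outcome: psychological profile and the dose of a co-analgesic. It is binary as used in Section 8.1.2, is known for every patient before allocation, and costs nothing to collect. With 22 per arm, the arms can differ by several PCS >20 patients by chance, and nothing in the design limits that gap or allows for it in the primary test.

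At stake are precision and how the result can be read. If the arms differ visibly in background steroid, readers will ask whether this shaped the result. With no pre-specified adjustment, any answer would come from an analysis chosen after the data were seen.

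**Working it through.** **Inputs from the documents.** 22 per arm; mean 390 and SD 208 for cumulated pain; a 50% reduction; two-sided 0.05; 80% power; 18 per arm before dropout (Section 7.1). Dexamethasone 0.3 or 1 mg/kg, rounded up to 10 mg (Section 8.1.2).

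**Assumptions (not in the documents).** Share with PCS >20: 20%, 30% or 40%, taken as K = 9, 13 or 18 of 44. Difference in cumulated pain between PCS groups: 0.5 SD = 0.5 × 208 = 104 units. Block size 4, read from the 2:2 wording.

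**1. The plan's sample size.** Effect = 0.5 × 390 = 195. By the normal formula, n = 2 × (1.960 + 0.842)² × (208/195)² = 17.9, so 18 per arm, as stated. With the t distribution, power is 78.0% at 18 and 85.9% at 22 per arm.

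**2. Dose ratio.** Nominal: 1/0.3 = 3.33. After rounding up, at equal body weight:

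| Weight | 0.3 mg/kg rule | 1 mg/kg rule | Ratio |
|---|---|---|---|
| 61 kg | 20 mg | 70 mg | 3.5 |
| 70 kg | 30 mg | 70 mg | 2.33 |
| 85 kg | 30 mg | 90 mg | 3.0 |
| 100 kg | 30 mg | 100 mg | 3.33 |

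Over 50 to 140 kg the ratio runs from 2.33 to 3.5.

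**3. Chance imbalance.** With K patients above 20, the number X in one arm is hypergeometric (44, K, 22), and the gap between arms is |2X − K|. The gap has the same parity as K: it is odd for K = 9 and 13, and even for K = 18.

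| K (share) | P(gap ≥ 5) | P(gap ≥ 6) |
|---|---|---|
| 9 (20%) | 0.132 | 0.021 |
| 13 (30%) | 0.185 | 0.045 |
| 18 (40%) | 0.124 | 0.124 |

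For K = 18, a gap of 5 or more means 6 or more. Simulating 11 blocks of 4 gave the same probabilities at K = 9 and 13 to within simulation error. Because of parity, P(gap ≥ 5) moves up and down between these points: over every K from 9 to 18 it lies between 0.069 (K = 10) and 0.215 (K = 17).

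**4. Shift in the arm difference.** Shift = (gap/22) × 104.
- Gap 5: 5/22 × 104 = 23.6 units.
- Gap 6: 6/22 × 104 = 28.4 units.
- Standard error = 208 × √(2/22) = 62.7, so the shifts are 0.38 and 0.45 SE, or 12% and 15% of 195.

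**5. Gain from adjustment.** The share of variance explained by the PCS stratum is p(1 − p) × 0.5². This is 0.040, 0.053 and 0.060 for p = 0.2, 0.3 and 0.4. The residual SD is 208 × √(1 − that share) = 203.8, 202.5 and 201.7. Power at 22 per arm becomes 87.3%, 87.7% and 88.0%. Charging one degree of freedom for the covariate lowers these by less than 0.1 point.

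**6. Effect of stratifying.** In permuted blocks of 4, only the last, incomplete block in a stratum can be unbalanced, and by at most 2. The gap in PCS >20 patients therefore cannot exceed 2 of 22, about 9 percentage points.

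**The case against.** The strongest defence is that blocked 1:1 randomisation with an unadjusted two-group test is valid. Dexamethasone is given before allocation under the same rule in both arms. Its effect, and that of PCS, forms part of the outcome variance that the standard error already reflects. This stands in full. A reader might infer that a PCS imbalance would confound the cryoneurolysis effect or inflate the type I error. The documents do not support that: allocation is random with respect to PCS.

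The effect is also modest. A shift of 0.38 to 0.45 SE is unlikely on its own to overturn a planned effect of 195/62.7 = 3.1 SE, though it could matter for a result near the significance threshold. Nor is a large gap the expected outcome; a realistic minority chance is the fair description.

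The prognostic gap between PCS groups is assumed in both size and direction. The higher dose goes with the higher score, so the two influences may partly offset each other. The VAS entry threshold, applied after dexamethasone, may narrow the gap further. Section 1.1 says psychological profile, not PCS, and ranks movement-evoked pain at 24 h as the best predictor once postoperative pain is considered. All of this stands. It limits the expected gain, but it is not a reason to leave the choice of adjustment open until after the data are seen.

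A reader might also take the steroid contrast to be more than threefold throughout. That is true of the nominal mg/kg figures, but at many body weights rounding brings it to threefold or less.

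Two features might seem to answer the point already. The two lists in Section 6.1 are not described as strata. The multivariate analysis in Section 7.2 names no covariate, although the full analysis plan that Section 7.2 promises could still do so.

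**Conclusion.** The point holds as an inexpensive improvement, not as a flaw in validity. A baseline factor that the protocol ties to background analgesia, and through psychological profile to pain, is used in neither allocation nor the primary analysis. At assumed shares of 20%, 30% and 40%, there is about a 12–19% chance that the arms differ by 5 or more PCS >20 patients. Such a gap would move the estimate by roughly 24–28 units if the PCS groups differ by 0.5 SD. The gain from adjustment is real but small: about 1 to 2 percentage points of power, plus a pre-specified answer to the question of background steroid. The dose rule, the eligibility criteria, the availability of PCS and the absence of a named factor or covariate are all read directly from the documents. The share, the 0.5 SD and the block size are assumptions.

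**What to change.** 1. In Section 7.2, or in the full analysis plan it announces, make the primary analysis a linear model (ANCOVA) of cumulated pain on treatment with PCS stratum (≤20 / >20) as a covariate. Fix this before unblinding. Cost: one degree of freedom; no new data, and the sample size stays at 44.
2. If the randomisation list has not yet been generated, also stratify it in Section 6.1 by the same cut. Cost: two strata to manage, PCS to be retrieved before the allocation code is drawn, and possibly one incomplete block per stratum. With blocks of 4, two incomplete blocks could at worst leave the arms at 24 and 20, which changes the standard error only from 62.7 to 208 × √(1/24 + 1/20) = 63.0.
3. If the list already exists, step 1 alone gives most of the benefit.
4. State in Section 6.1 what the two lists are for, so that they are not mistaken for strata.

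No change to dosing is proposed.

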6.2 Blinding

The patient, the investigators performing study-specific assessments, and the sponsor will all be blinded to the intervention allocation, until all data processing is finished. However, one anesthetist performing the intervention will be unblinded to the allocation.

Sealed coding-envelopes containing data on randomization are stored in a locked cabinet at the Dept. of Anesthesiology, Hvidovre Hospital. If an unblinding of a randomized patient is deemed necessary by the attending physician, to secure health and patient-safety, unblinding will be made by opening the sealed patient-specific randomization envelope, containing set patient's allocation. The on-site investigator can always also be contacted to assist in unblinding and guidance. In case of unblinding, the reason for unblinding is noted, dated, and signed by the investigator in the specific patient CRF.

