8.5 Study location

The inclusion will take place at the Dept. of Orthopedic Surgery, Arthroplasty unit at Hvidovre Hospital, Capital Region of Denmark. Study personnel include employees from the Dept. of Orthopedic Surgery, the Surgical Wards and the Dept. of Anesthesiology, at Hvidovre Hospital.

The sponsor and investigators are employees at the Research Unit at the Dept. of Anesthesiology, Hvidovre Hospital.

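### Section 6.1's 2:2 blocks, naturally read as constant blocks of four, would make about a third of assignments certain in advance to an operator who knows all the earlier ones

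*Combined protocol and SAP*

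**What the plan says.** Section 6.1 (Randomization) states that "a randomization will be carried out using 2:2 block-randomization", with "half of which will be allocated to the sham-group and the other half to the cryo-group". An online service generates the codes, which are imported to REDCap. The section mentions no varying block size, no stratification, and no restriction on who may know the block size. Section 4.2 sets the total at 44, with 22 per arm.

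On masking, Section 6.1 says that "the patient and all personnel involved in study-specific assessments will be blinded to the allocation", while Section 6.2 says that "one anesthetist performing the intervention will be unblinded to the allocation". Section 8.5 places inclusion at one site: "The inclusion will take place at the Dept. of Orthopedic Surgery, Arthroplasty unit at Hvidovre Hospital, Capital Region of Denmark".

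On custody, Section 6.1 says: "Two lists containing the unique randomization codes will be made and stored at the Dept. of Anesthesiology, Hvidovre Hospital". Section 6.2 keeps sealed patient-specific envelopes in a locked cabinet in the same department. Section 8.5 adds: "The sponsor and investigators are employees at the Research Unit at the Dept. of Anesthesiology, Hvidovre Hospital". Section 13.2 has consent collected by the investigator or a research nurse, with other research collaborators as backup. It neither names nor excludes the operator.

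**The concern.** In a block of four with two places per arm, the rest of the block is known once one arm's two places are used. This happens after two like assignments, or at the latest after three. A single site and an unstratified list mean one sequence, and one unblinded operator can accumulate all of it.

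The safeguard at stake is allocation concealment. Entry depends on a self-rated walking VAS of at least 45 in a 20 to 28 hour window (Section 5.1), and the intervention follows at 20 to 32 hours (Section 8.2). If someone with a say in whether or when a patient enters knew the next assignment, that knowledge could influence who is enrolled. The plan does not bar the operator from such a role, and it does not say at what moment, or to whom, an assignment is revealed.

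**Working it through.** **Inputs.** Block composition 2:2, read as size four (Section 6.1). Total 44 (Section 4.2), so 44 / 4 = 11 whole blocks, which fits that reading. One unblinded operator (Section 6.2) and one site (Section 8.5). The plan gives no predictability figure of its own to reproduce.

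**Assumptions.** The observer knows the block size, the block boundaries and every earlier assignment. An assignment is certain when one arm's two places in the current block are already used.

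**Certain assignments, blocks of four.** There are six equally likely orderings.
- AABB and BBAA (2 of 6): positions 3 and 4 are certain, so 2 certain assignments.
- ABAB, ABBA, BAAB and BABA (4 of 6): only position 4 is certain, so 1 certain assignment.

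Expected per block = (2×2 + 4×1)/6 = 1.33, and 1.33/4 = 33.3%. Over 11 blocks the mean is 11 × 4/3 = 14.7. The minimum is 11 × 1 = 11 (25%) and the maximum 11 × 2 = 22 (50%). The variance per block is 2/9, so the SD over 11 blocks is √(11 × 2/9) = 1.6.

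**Best guess, blocks of four** (always guess the arm with more places left).
- Position 1: 1/2.
- Position 2: 2/3.
- Position 3: tied with probability 2/3, otherwise certain, so 2/3 × 1/2 + 1/3 × 1 = 2/3.
- Position 4: 1.

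Mean = (0.500 + 0.667 + 0.667 + 1)/4 = 70.8%, against 50% for an unpredictable list.

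**Varied block sizes.** These figures are simulated: sizes equally likely, the list cut at 44, and an observer who knows the set of sizes and all earlier assignments but not each block's size.

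| Block sizes | Certain | Best guess right |
|---|---|---|
| 4 only | 33% | 71% |
| 4 and 6 | about 6% | about 69% |
| 4, 6 and 8 | about 2% | about 68% |

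**Lists constrained to total exactly 44.** I repeated the simulation with 4,000 lists per setting, drawing sizes that sum to 44. Certain assignments are again about 6% (4 and 6) and 2% (4, 6 and 8) if the observer ignores the total. They are about 9% and 6% if the observer also uses the fact that the last block must close at 44. The best-guess rates stay at about 69% and 68%.

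**Arm sizes if the total is not constrained.** With a largest block of 8, 40 patients may be balanced 20/20 and the next four all fall in one arm, giving 24/20.

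**The case against.** The strongest reply is that predictability does no harm without a route to act on it, and the documents show no such route. The only person shown to know past assignments is the operator, who is given no part in screening, consent or scheduling. Entry turns on the patient's own VAS rating in a narrow window, and Section 13.1 requires a log of patients who decline. The list comes from an external service and the envelopes are sealed. All of this stands, and it limits the point to a minor one.

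The premises are also softer than they look. Section 6.1 does not call the blocks fixed, and Section 6.2 does not say outright that the same anesthetist treats all 44 patients. Both are natural readings and are carried here as assumptions. Who may open the stored lists is not stated. If the operator could read them, varying the blocks would not help.

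Four stronger readings are tempting, and the documents do not support them:
- **That one emergency unblinding exposes the block.** One known assignment leaves three places, two of them for the other arm. Each remaining block-mate moves from 1/2 to 2/3, not to certainty.
- **That lasting numbness identifies the arm to assessors.** Both arms receive ropivacaine (Sections 4.1 and 8.2.2). The documents give no figure for how well later numbness separates the arms.
- **That an assessor's guess contaminates the primary outcome.** Patients enter the days 2 to 7 ratings themselves, electronically or in a diary (Section 8.3). A guess has no direct route into them.
- **That all staff will know the block size from the protocol.** Section 10.3 promises role-specific procedural descriptions and an accessible overview. It does not say that everyone reads Section 6.1.

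Finally, the gain is partial. Varying the blocks removes most of the certainty but lowers the best-guess rate by only two to three percentage points.

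**Conclusion.** The point holds as avoidable predictability. With constant blocks of four, an operator who treats all patients in sequence and knows the block boundaries can be certain of a third of assignments on average: about 15 of 44, and never fewer than 11 or more than 22. The best guess is right 71% of the time.

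A reader might infer that concealment is broken or that selection bias will follow. The documents do not support that, because they are silent on whether the operator influences who enters or when. The silence leaves the route unprotected; it does not show that the route is used. The missing statement of when an assignment is revealed is a secondary gap in detail. This is a minor improvement, worth making because it costs so little.

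**What to change.** Generate the list with block sizes varied at random, for example 4 and 6, or 4, 6 and 8. Draw them so that they total 44 with 22 per arm: five blocks of 4 and four of 6 give 20 + 24 = 44, and three of 4, four of 6 and one of 8 give 12 + 24 + 8 = 44. Have someone outside the enrolling team produce the list and hold the sizes in a restricted file. In Section 6.1, replace the 2:2 wording with a statement that block sizes vary and are withheld. Add that the operator takes no part in eligibility, consent or scheduling, and that an assignment is revealed only after consent and registration in REDCap.

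The cost is minor list-generation work and two or three sentences. Constraining the total matters because Section 17.1 budgets exactly 22 probes. Without it the arms could end at 24/20, which in the worst case needs two more probes (2 × 3,500 = 7,000 DKK). The statistical loss would be negligible: the equivalent equal-arm size is 2 × 24 × 20 / 44 = 21.8 per arm, against 22 planned and 18 required in Section 7.1. The price of constraining is the slightly higher share of certain assignments, about 6 to 9%, for someone who exploits the known total.
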